## **1.0 BACKGROUND AND RATIONALE**

### **1.1 Study Synopsis**

This is a study that will evaluate the utility of a scatter reduction technique in reducing dose and increasing the sensitivity of stationary digital chest tomosynthesis (s-DCT) in the detection of lung lesions. Digital tomosynthesis is an imaging modality that produces 3D sectional information using x-ray projections acquired over a limited scanning angle. Scatter is known to be the primary source of image degradation in x-ray based imaging.

We have developed an approach that measures scatter through a low dose (3% of the conventional scan) scatter measurement technique. Preliminary studies have shown that scatter reduction in DCT can significantly improve quality. We plan to characterize the reader confidence in lung nodule detection in our scatter corrected chest tomosynthesis imaging approach as compared to our conventional chest tomosynthesis.

Fifty (50) patients who have undergone a clinical non-contrast CT with lung nodules will be asked to have an s-DCT (scan) within 4 weeks (+/- 2 week) of their clinical CT with no intervening procedures or therapies (i.e. biopsy of lung nodules). We will then perform a reader study to evaluate the radiologist reader confidence in images generated from the scatter reduction technique versus more conventional chest tomosynthesis imaging.

### **1.2 Lung Cancer and Screening**

Lung cancer continues to be the leading cause of cancer deaths in the world. Over 200,000 new cases of lung cancer were identified in 2010 in the US, and lung cancer death exceeds the total estimated deaths from breast, prostate and colon combined. Conventional chest radiographs are known to perform poorly in screening and identification of small stage I cancers due to the small lesion size and poor conspicuity. The low dose-CT based National Lung Screening Trial was published in 2011, and demonstrated that there was an overall 20% reduction in lung cancer mortality in the low dose CT screening group in patients at high risk of lung cancer as compared to conventional radiographs. Low dose CT was estimated to provide 1.5 mSv, at roughly 20 to 30 mAs for an average sized patient. Conventional chest CT is estimated to be approximately 8 mSv. This lower dose results in a lower radiation risk to patients.

### **1.3 Chest Tomosynthesis**

Digital chest tomosynthesis (DCT) is a three-dimensional imaging technique that provides reconstruction planes from a limited-angle series of projection images. Clinical tomosynthesis applications include chest imaging [3-10], angiography [11], joints imaging [12], dental imaging [13], and breast imaging[3, 14, 15]. Compared to conventional chest radiography, DCT results in improved visibility of normal structures such as vessels, airway and spine. By reducing visual clutter from overlying normal anatomy, it also enhances detection of small lung nodules[2]. DCT has better resolution than CT in the plane of the image (but worse resolution in the depth direction) at a significantly lower radiation dose and cost [2]. In the current commercial systems, the projection images are collected by mechanically moving a single x-ray source to different

viewing angles, as illustrated in Figure 1. Two DCT systems are currently commercially available, the GE VolumeRAD and Shimadzu RADspeed. In the GE VolumeRAD [16, 17] system, the x-ray generator is mounted on a crane moving vertically with a variable source-to-detector distance of 180cm. A typical tomosynthesis scan includes 61 projections over 30° in 10 seconds

#### 1.4 Chest Tomosynthesis for Lung Cancer Screening

A number of groups have explored the use of DCT for the screening and the identification of pulmonary nodules. The key attraction of DCT is that it exposes patients to lower doses of radiation than CT. As shown in Table 1, in terms of dose, DCT is typically 10 to 50 times lower than CT, and 3 to 5 times lower than 2D chest radiography (CR). In terms of diagnostic sensitivity and accuracy DCT is significantly better than CR, and is approaching that of CT. The reported effectiveness, as measured by sensitivity, of the GE system, as measured by the AUC (Area under Curve) using CT as the gold standard, varies from 0.73 to 0.96. [1] [18] [19]. The reported variation in AUC is partially attributed to patient motion during the scan. A recent study by Kim et al shows that when no respiratory motion artifacts are present, the detection performance of DCT for nodules (4–10 mm) is significantly better than that of CR; whereas there is not a significant difference in cases with motion artifacts. Using the Shimadzu RADspeed, which has a scanning time of 5s, Yamada et al reported AUC as high as 0.93 [20]. These results indicate that reducing image blurring due to respiratory motion is critical for improving the diagnostic accuracy of DCT. Patients with diseases of the lung, such as COPD or emphysema are severely compromised in their ability to hold their breaths for an extended period of time and consistently on command. *Because of the long travel distance (~1m), heavy weight of the x-ray generator, and the precision required, further reduction of the scanning time is difficult even if the x-ray source can produce sufficient flux.*

**Table 1:** Comparison of dose, scan time, diagnostic accuracy between CT, CR, DCT, and the UNC stationary DCT systems.

	CT	CR	GE DCT	Shimadzu DCT	UNC s-DCT
Dose (mSv)	3~10	0.02~0.06	0.06~0.2	0.2	~0.2
Dose (mAs)	130-300	~1	3-15	3	3
Scan time (s)	~2s	< 1s	10s	5s	2s
Coverage (deg)	360	0	30	40	20 ~ 40
# of views	~1000	1	60	74	60
AUC	1.0	0.7~0.77	0.73~0.96[1]	0.93[20]	TBD
AUC with motion			0.73[19]		
AUC without motion			0.85 [19]		

## **1.5 Rationale**

The proposed research, if successfully implemented, will result in a low-dose, low-cost, and highly effective method for screening of lung nodules, which may result in earlier treatment of patients with early stage lung cancer. Using the scatter corrected s-DCT system the imaging dose for a full tomosynthesis scan is expected to be only 10% of that from a low-dose CT, and half of a conventional tomosynthesis scan. Beyond lung cancer screening, the low-dose and sensitive 3D lung imaging modality will likely to find applications in areas such as monitoring of pediatric cystic fibrosis patients where reduction of imaging dose is critical.

The proposed study is a close collaboration between 2 clinical researchers ([name], MD/PhD, [name]) utilizing the technology invented by two basic scientists ([name], and [name]) at UNC. It leverages the resources from several ongoing R&D programs in our lab on new imaging and radiotherapy devices based on the CNT x-ray source array technology, including the stationary digital breast tomosynthesis[25, 26] and microbeam radiation therapy systems[27] that are also invented by our team. We believe the success of this pilot project will lead to a larger scale multidisciplinary project to translate the low-dose stationary digital chest tomosynthesis technology to a clinically viable modality for lung cancer screening.

## **2.0 STUDY OBJECTIVES**

### **2.1 Primary Objectives**

Evaluate the reader confidence in the evaluation of s-DCT image with and without PSSC scatter correction.

### **2.2 Secondary Objectives**

The sensitivity of the scatter corrected s-DCT system to conventional s-DCT in the detection of lung nodules.

### **2.3 Primary Endpoint**

The reader confidence in the interpretation of scatter corrected s-DCT images to conventional s-DCT images

## **3.0 PATIENT ELIGIBILITY**

### **3.1 Inclusion Criteria**

- 3.1.1 Patients with a known lung lesion(s)
- 3.1.2 Patients having undergone a chest CT
- 3.1.3 Patients 18 years of age and older
- 3.1.4 Patients able to provide informed consent

### **3.2 Exclusion Criteria**

**3.2.1** Patients unable to provide consent

**3.2.2** Patients who may not fit on a 35 x 35 detector (BMI > 35).

[figure not shown]
**3.2.3** Planned procedures or therapies during study (in between SOC scans and study scan on s-DCT) (biopsy or excision of lung lesion)

**3.2.4** Institutionalized patient (prisoner or nursing home patient)

## **4.0 STUDY PLAN**

### **4.1 STUDY SCHEMA**

This is a one arm study of 50 patients with one or more lung nodules who have had standard imaging (chest CT) who consent to undergo an experimental scatter correction s-DCT to characterize the number and extent of lung nodules. This experimental scan will be compared with CT to define the sensitivity of lung nodule detection among this group. The CT scan is used as the gold standard to assess for the presence of a nodule and will be interpreted by consensus to identify the target nodule for each case.

### **4.2 Duration of the Study**

It is anticipated that the total study duration encompassing recruitment, enrollment, and data analysis will take approximately 1 year. Patient participation will last approximately 1 to 3 weeks.

### **4.3 Study Procedures**

#### **4.3.1 Enrollment/Recruitment**

We will review upcoming clinical chest CT studies for lung nodule follow-up. We will ask patients to participate in this study to evaluate the utility of the scatter reduction approach for stationary digital chest tomosynthesis (s-DCT) machine, using the standard of care chest CT for comparison.

Once a patient has been identified, or we have collaborated with the treating clinic regarding the eligibility of a subject, the patient will be approached by a coordinator from Radiology to assess interest in participation. The coordinator will either go to the treating clinic, or will call the patient at home.

If the patient is interested in participation, he/she will be consented either then (in their treatment clinic) or when he/she arrives to have his/her s-DCT, but prior to any study procedures. Review of the consent will take place in the privacy of an exam room, or when possible, a sample consent will be sent to the patient via email prior to arriving for the scan to allow for ample review.

#### **4.3.2 Research Imaging**

##### **4.3.2.1 Imaging Procedures**

The study scan, s-DCT and correction scan, will be performed within two weeks of his/her clinical evaluations by chest CT and x-ray. The study scan may be done within 2 weeks prior or two weeks following standard of care imaging. There cannot be any intervening therapies or procedures (i.e. biopsy or excision of lesions) done in between the SOC imaging and the s-DCT.

All patients will have a breath held s-DCT scan in an anterior-posterior direction. Images will be reconstructed off-line and transferred for review on conventional PACS workstations. Images will be reviewed by radiologists.

#### **4.3.3 Reader Study**

Three thoracic imaging specialty radiologists will be asked to separately evaluate the two sets of s-DCT images in a paired reader study. The radiologists will be presented with deidentified images from one modality (either with or without PSSC correction), then asked to identify the lesion and then determine a likelihood of malignancy based on the overall image set. A likelihood of malignancy score (1 to 10) will be initially assigned by the reader. The reader will then be given the deidentified images from the second modality, and their relative confidence in interpretation of the first modality as compared to the second will be evaluated on a 7 point scale. A washout period of four weeks will be provided and the images reviewed in reverse. Confidence scores in the evaluation of lung lesions, locations and involved structures will also be assessed. The CT scan is used as the gold standard to assess for the presence of a nodule and will be interpreted by consensus to identify the target nodule for each case.

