### **7.2 Sample Size and Accrual**

Assuming 50 cases are available for the comparison, and the standard deviation of the average reader score to be 2 (the range of the score is from +3 to -3), we will have at least 80% power to detect 0.7 confidence score of using scatter correction over without correction. In the data analysis, we will fit a linear mixed effect model with the confidence score as the outcome and a constant intercept. The working correlation matrix among readers is assumed to be compound symmetry. We will estimate grand mean from this model and test whether the mean confidence score is different from zero.

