**10.0 APPENDICES**

**Scatter Corrected versus Uncorrected s-DCT  
 Reader Study**

Study # \_\_\_\_\_

Reader # \_\_\_\_\_

Date \_\_\_\_\_

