**If the confidence rating is 3 or greater (3, 4 or 5)**

**Lesion location (mark on figure):**

**Lesion size (measured in the coronal plane):**

**Presence of calcifications: Y / N**

**Comparing both modalities:**

**2. Scatter Corrected s-DCT versus Uncorrected: Shape/Morphology**

-3	-2	-1	0	+1	+2	+3
significantly less confident in the Chest Tomo representation	less confident in the CHEST TOMO representation	slightly less confident in the CHEST TOMO representation	have the same confidence in the CHEST TOMO	slightly more confident in the CHEST TOMO representation	more confident in the CHEST TOMO representation	significantly more confident in the CHEST TOMO representation

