**2. Scatter Corrected s-DCT versus Uncorrected: Calcifications**

-3	-2	-1	0	+1	+2	+3
significantly less confident in the CHEST TOMO representation	less confident in the CHEST TOMO representation	slightly less confident in the CHEST TOMO representation	have the same confidence in the CHEST TOMO	slightly more confident in the CHEST TOMO representation	more confident in the CHEST TOMO representation	significantly more confident in the CHEST TOMO representation

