**3. Scatter Corrected s-DCT versus Uncorrected: architectural distortion**

-3	-2	-1	0	+1	+2	+3
significantly less confident in the CHEST TOMO representation	less confident in the CHEST TOMO representation	slightly less confident in the CHEST TOMO representation	have the same confidence in the CHEST TOMO	slightly more confident in the CHEST TOMO representation	more confident in the CHEST TOMO representation	significantly more confident in the CHEST TOMO representation

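### Masking of readers to scatter-correction status is not stated, and the reader form gives its scores a direction only by naming corrected versus uncorrected

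*Combined protocol and SAP*

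**What the plan says.** Section 4.3.3 describes the reading: "The radiologists will be presented with deidentified images from one modality (either with or without PSSC correction), then asked to identify the lesion". After the second set is shown, "relative confidence in interpretation of the first modality as compared to the second will be evaluated on a 7 point scale". Then: "A washout period of four weeks will be provided and the images reviewed in reverse". Section 7.4 uses the term de-identified for the chest CT as well as for both tomosynthesis sets.

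The reader form in the Appendices is titled "Scatter Corrected versus Uncorrected s-DCT". Its three signed items are headed "Scatter Corrected s-DCT versus Uncorrected: Shape/Morphology", "Scatter Corrected s-DCT versus Uncorrected: Calcifications" and "Scatter Corrected s-DCT versus Uncorrected: architectural distortion". The scale anchors under each heading speak only of the chest tomo representation, a description that fits both sets.

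Section 2.3 makes reader confidence the primary endpoint. Section 7.2 powers the study to "detect 0.7 confidence score of using scatter correction over without correction", and Section 7.3 tests whether the grand mean of the confidence scores exceeds zero.

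**The concern.** The primary outcome is a judgement about which of two image sets inspires more confidence. Section 1.1 already reports that scatter reduction improved quality in preliminary work, so an expectation in favour of the corrected set is plausible. If readers know or believe they know which set is corrected, that expectation can move the score with no difference in what the images show.

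Nothing in the plan would remove such a shift. The Section 7.3 model contains a grand mean and a random intercept, so a constant shift falls entirely into the parameter being tested and cannot be separated from a true effect afterwards. The second reading in reversed order balances order effects only. Any protection has to be applied when the images are read.

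**Working it through.** **1. Is masking stated?** Sections 4.3.3, 7.1, 7.3 and 7.4 and the Appendices were read for it. None says that readers are masked to correction status, that processing labels are removed, or that the set shown first is randomised or concealed. Because Section 7.4 applies de-identification to the CT too, the word is best read as removal of patient identity.

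**2. What does the form require?** The anchors do not say which set is being rated, since both are chest tomosynthesis. The heading alone supplies the direction, and it does so by correction status. Section 4.3.3 supplies a different direction, by position: first shown against second shown. Positional scoring can be done masked, with the sign assigned later. The form does not follow that rule, and no section describes recoding from position to correction status. Sections 7.2 and 7.3 make the intended direction clear (corrected over uncorrected), so procedure and form need to be aligned to it.

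**3. Why reversal does not help.** Code scores as corrected minus uncorrected. Let e be an expectation shift and o an order shift. One session gives e + o, the other e - o, and the average is e. For example, e = o = 0.25 gives 0.50 and 0.00, average 0.25: the order effect cancels and the expectation shift stays.

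**4. The plan's own figure.** Inputs from Section 7.2: n = 50, SD of the average reader score 2, difference 0.7. SE = 2/√50 = 0.283. One-sided power at 0.05 is Φ(0.7/0.2828 - 1.645) = Φ(0.830) = 79.7%, which matches the stated 80%. The two-sided equivalent is Φ(2.475 - 1.960) = 69.7%. The one-sided setting is therefore used first below. Section 7.2 is worded two-sided and Section 7.3 one-sided; that is a separate matter, and both are shown.

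**5. Illustration of sensitivity.** Assume no true effect and a mean shift of b points toward correction. The values of b are assumptions; the documents give none. The chance of declaring correction superior is P(Z > 1.645 - b/SE) one-sided, or P(Z > 1.960 - b/SE) for the upper tail of a two-sided test.

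| Assumed shift b | One-sided 0.05 | Upper tail, two-sided 0.05 |
|---|---|---|
| 0 | 5.0% | 2.5% |
| 0.10 | 9.8% | 5.4% |
| 0.20 | 17.4% | 10.5% |
| 0.25 | 22.3% | 14.1% |
| 0.30 | 28.0% | 18.4% |

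The shift that doubles the one-sided rate is (1.645 - 1.282) × 0.2828 = 0.103 points, on a scale with one-point steps.

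**The case against.** The strongest reply is that the form names the comparison under study, not which displayed set is corrected, and that the positional rule in Section 4.3.3 is compatible with masked reading. That is right. A reader of the plan might infer that the radiologists are unmasked, or that the form tells them which set is which. The documents do not support either inference. What stands is narrower: masking is not stated, and the form's headings do not fit scoring by a reader who does not know the status.

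A second reply is that the size of any bias is unknown. This also stands. The percentages above would follow from any assumed shift and do not show that one exists. It would be wrong to read 22% as the plan's present error rate. No section says whether the three readers are investigators or share the expectation voiced in Section 1.1.

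Third, the plan collects measures that are not scored as corrected versus uncorrected: a malignancy score given before the second set is shown, a lesion-presence rating from 1 to 5, and sensitivity against a consensus CT reading. These could support or contradict the primary result, but they do not protect the primary score itself.

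Finally, correction is meant to change how the images look, and readers see both sets of the same patient. Masking may therefore be incomplete. That limits the benefit of the change but does not remove the case for a cheap safeguard in what Section 1.5 calls a pilot project.

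**Conclusion.** The point holds in limited form and should be addressed. The plan does not state that readers are masked to correction status, and the form as written needs the reader to know or guess that status in order to sign a score. For a subjective primary score tested against zero, any expectation favouring correction would pass straight into the tested mean, and the reversed reading would not remove it.

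The size is unknown. On the plan's n = 50 and SD 2, with no true effect and a shift constant across sessions, an assumed 0.10 points would take the one-sided false-positive rate from 5% to about 10%, and 0.25 points to about 22%. The documentary finding does not depend on these figures. Confidence is medium, because the actual reading set-up may be better than the text and the yield of masking is uncertain.

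**What to change.** - **Section 4.3.3:** state that readers are masked to correction status. Replace the comparison of first with second modality by a comparison of Image A with Image B.
- **Images and form:** present the sets as Image A and Image B. Remove processing labels from image headers and from the form's title, item headings and anchors; the anchors should say Image A compared with Image B.
- **Allocation:** assign A/B and the set shown first by a computer-generated list per case and reader, with the order reversed in the second session as already planned.
- **Key and recoding:** keep the key with someone who does not handle the reader scores until they are locked. The documents do not say who will enter those scores, so this role has to be named. After lock, recode every score to corrected minus uncorrected, the direction in Sections 7.2 and 7.3, before fitting the Section 7.3 model.

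The cost is small set-up work: one list, relabelled image series and a reworded form. No extra patients, scans or readers are needed, and the sample-size inputs do not change. The downside is that correction may be recognisable from image appearance. If masking removed half of an assumed 0.25-point shift, 0.125 points would remain and the one-sided rate would be P(Z > 1.645 - 0.125/0.2828) = 11%, against 22% with the full shift.

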### **7.3 Data Analysis Plans**

The study will be performed as a reader confidence study. For each comparison, the average confidence scores and the corresponding standard deviations will be reported. Furthermore, to test whether the mean confidence score is larger than zero, a linear mixed effect will be used to analyze data, where the outcome variable is the confidence scores collected in this study and only a grand mean parameter is in the independent list. Additionally, a random intercept is used in the model to account for the correlation among readers when reading the images from the same patient. The Wald's test based on model fit will be used to test whether the grand mean parameter is larger zero. When the p-value from this test is less than 0.05, it will be concluded that there exists significant evidence that readers have more confidence with the s-DCT scatter corrected modality compared to the conventional s-DCT.

The reader preference study form (including both primary and secondary evaluations) is located in the Appendix.

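### Section 4.3.3 scores the first-shown set against the second, but the form and Sections 7.2 and 7.3 need corrected against uncorrected, so uncorrected-first scores can enter the primary analysis with the wrong sign

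*Combined protocol and SAP*

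**What the plan says.** Section 4.3.3 is the only description of the reading procedure. The reader is first "presented with deidentified images from one modality (either with or without PSSC correction"), then sees the other set, and "their relative confidence in interpretation of the first modality as compared to the second will be evaluated on a 7 point scale". It adds: "A washout period of four weeks will be provided and the images reviewed in reverse".

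The Appendix form carries a scale from -3 to +3. Its title and its three comparison items (shape/morphology, calcifications, architectural distortion) set scatter-corrected against uncorrected images, whatever the order of showing. The response anchors, however, speak only of more or less confidence in the chest tomo representation. Section 1.1 uses chest tomosynthesis for both sets: "our scatter corrected chest tomosynthesis imaging approach as compared to our conventional chest tomosynthesis". In the text available, the form header records study number, reader number and date.

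Section 7.2 fixes the direction of the effect: "we will have at least 80% power to detect 0.7 confidence score of using scatter correction over without correction". In Section 7.3 "the outcome variable is the confidence scores collected in this study and only a grand mean parameter is in the independent list", and a Wald test is used "to test whether the mean confidence score is larger than zero". A significant result is read as more confidence with correction. On the form, Section 7.3 says only this: "The reader preference study form (including both primary and secondary evaluations) is located in the Appendix".

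**The concern.** The sign of this score decides the trial's primary conclusion, and the plan gives two rules for it. They agree when the corrected set is shown first. When the uncorrected set is shown first, first against second is uncorrected against corrected, so every nonzero score reverses. If the reversal after washout swaps the order of the sets, uncorrected-first readings arise by design.

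Nothing downstream catches this. Section 7.3 analyses the scores as collected, with a grand mean and no order term. No re-signing rule is stated. The form as shown does not record which set came first, so scores could not be re-signed later from the form alone.

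Two errors are possible. A real preference for correction can be diluted, cancelled or reversed. And if all scores are coded by order, a tendency to favour whichever set is seen first is tested in place of the preference.

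**Working it through.** **Inputs from the plan.** 50 cases, SD of the average reader score 2, effect 0.7 and range -3 to +3 (Section 7.2); level 0.05 and a test for a mean larger than zero (Section 7.3); three readers and a repeat in reverse (Section 4.3.3).

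**The plan's own power.** SE = 2/√50 = 0.283. One-sided power = Φ(0.7/0.283 - 1.645) = Φ(0.83) = 79.7%, which matches the stated 80% to rounding. A two-sided test gives Φ(0.7/0.283 - 1.960) = 69.7%, so the stated figure fits only the one-sided test of 7.3. It also requires every score to be oriented to corrected versus uncorrected.

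**Effect of mixed signs on the mean.** Let u be the share of scores given with the uncorrected set first, and q the share of those kept in the 4.3.3 direction. The documents give neither. Each such score contributes -0.7 instead of +0.7 on average, so

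expected mean = 0.7(1 - 2uq).

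**Two sessions, both scored, order swapped (u = 1/2).** The mean is 0.7(1 - q). Holding the SD at 2, power is Φ(0.7(1 - q)/0.283 - 1.645). In practice the SD shrinks too, because a flipped score also cancels part of the patient's own effect. Power was therefore simulated as well: 20,000 trials per cell, 50 cases, 3 readers, 2 orders, random-intercept Wald test, one-sided 0.05. With residual SD s (assumed), patient variance was 4 - s²/6, so that the average of a case's six readings has SD 2.

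| q | Mean | Power, s = 1 | Power, s = 0.5 to 2 | Power, SD held at 2 |
|---|---|---|---|---|
| 0 | 0.70 | 79% | 80% | 80% |
| 10% | 0.63 | 78% | 78% | 72% |
| 25% | 0.53 | 75% | 73-76% | 58% |
| 50% | 0.35 | 66% | 58-69% | 34% |

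For q from 10% to 50%, the last column is an upper bound on the loss. At q = 100% the mean is 0 and simulated power is about 0% (s = 1). This is below the nominal 5% because patient effects cancel between sessions while the model counts them as residual noise.

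**By reader (s = 1).** If 0, 1, 2 or 3 of the three readers use the 4.3.3 rule throughout, the mean is 0.70, 0.47, 0.23 or 0.00, and power is 79%, 78%, 57% or 0%.

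**One session only (s = 1).** Suppose 12, 25 or 38 of the 50 cases are shown uncorrected-first, so u = 0.24, 0.50 or 0.76.
- q = 50%: mean 0.53, 0.35, 0.17; power 64%, 42%, 19%.
- q = 100%: mean 0.36, 0, -0.36; power 34%, 4%, 0%.

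**First-shown bias b, no true preference, two sessions.** If every score is order-coded, b enters with the same sign in both orders and the expected mean is b. If every score is oriented, b enters as +b and -b and cancels.

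| b (assumed) | False claims, s = 1 | s = 0.5 to 2 |
|---|---|---|
| 0.10 | 3% | 0.2-9% |
| 0.15 | 17% | 10-18% |
| 0.20 | 44% | 32-57% |
| 0.25 | 75% | 47-95% |

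Oriented scores give about 5% (5.5% at b = 0.10 and 5.1% at b = 0.25, s = 1).

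**Bounded scale.** Rounding and clipping to -3 to +3 (s = 1) changes little. Power is 77%, 73% and 64% at q = 10%, 25% and 50%. False claims are 4%, 16%, 40% and 69% at the four values of b.

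**The case against.** The best counter-argument is that one clause in 4.3.3 stands against everything else. The objective, the sizing effect, the decision rule, and the form's title and item headings all compare corrected with uncorrected, and 7.3 says the form includes the primary evaluation. Section 4.3.3 assigns no plus or minus, so the clause may only describe the workflow. Study staff could keep a presentation list, and the form's date separates sessions four weeks apart, so re-signing might be possible. The size rests on inputs that the documents do not give.

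Much of this stands. The form's direction is probably the intended one, and if it is followed throughout, the analysis is unaffected. Occasional mis-signing costs little power: one reader of three on the 4.3.3 rule leaves it at 78% (73-79% over residual SD 0.5 to 2), although the estimate still falls by a third.

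But the intention has to be inferred. Section 7.3 says where the form is and what it contains, not that it overrides 4.3.3. The anchors do not settle the direction, and the documents mention no presentation list. A reader who follows the written procedure can give positive scores to the first-shown set without departing from the protocol.

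**Conclusion.** The concern holds. The contradiction is certain from the text; its effect depends on how readers score. It assumes that under 4.3.3 a positive score favours the first-shown set, which is the natural reading but is not stated. The two-session figures also assume that the reversal swaps the sets and that both sessions are analysed.

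On those assumptions the consequence runs from none, if the form headings are always followed, to complete loss of a true 0.7 benefit, if 4.3.3 is always followed. With one session and mostly uncorrected-first cases, the mean can turn negative. Order-coded scores can also turn a modest first-shown bias into a false claim well above the 5% level. Because a stated rule can reverse the sign of the primary outcome, this must be corrected, preferably before any reading, since the form shown does not capture order.

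**What to change.** 1. In Section 4.3.3, replace the first-against-second clause with: *In every session the analysed score is oriented so that positive values favour the scatter-corrected set, whichever set was shown first.*
2. Reword the form anchors to name the image set being favoured. If readers are not told which set is corrected, use a coded label that is decoded before analysis.
3. Add a form field for which set was shown first.
4. In Section 7.3, add: *All scores are oriented to corrected versus uncorrected before the model is fitted, and the mean is also reported by order of presentation.*

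The cost is one sentence in each of two sections, new anchor wording, one form field, and IRB approval of the amendment under Section 8.4. No extra patients, scans or readers are needed. If the form's direction was always intended, the edits simply record that.
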